6.6 Pharmacokinetics

6.6.1 Collection of pharmacokinetic samples

Venous blood samples for determination of concentrations of AZD9291 and its metabolites (AZ5104 and AZ7550) in plasma will be taken at the times presented in Table 5. Discussions will be required with the AZ PK representative as to any effect on the PK sample schedule if dose interruption occurs within 3 days of PK sampling. The date and time of collection of each sample and the date and time of dose will be recorded.

Table 5 PK blood sample schedule												
Time relative to Dose		Dose E	scalati	on only	1	All patients						
		Single	Dosing	Cycle	0	Multij	ple Dosin	g Cycle 1	Multiple Dosing Cycle 2			
	D1	D2	D3	D4	D6	D1	D8	D15	D1			
Pre-dose	X					Х	X	X	Х			
1h	Х								Х			
1.5h	Х								Х			
2h	Х								Х			
4h	Х								Х			
6h	Х								Х			
8h	Х								Х			
10h	Х								Х			
12h	X								Х			
24h		Х							X (D2, pre-dose)			
48h			Х									
72h				Х								
120h					Х							
At time of biopsy								X ^a				

a Cycle 1 Day 15 predose PK sample collected for all patients. Collection of the Cycle 1 Day 15 "at time of biopsy" PK sample is only required if biopsy taken and, where optional, is feasible to do so

A 5min window will be allowed for samples taken at 1h; a 10min window for samples taken at 1.5-10h; a 1h window for samples taken at 12h and 24h, a 2h window at 48h,-72h and a 24h window at 120h.

The timing of the pharmacokinetic samples may be adjusted during the study, dependent on emerging data, in order to ensure appropriate characterisation of the plasma concentration-time profiles. The total number of samples and the total volume of blood taken from each patient will not exceed that detailed in Section 6.9.1. Residual samples may be analysed for exploratory biomarkers.

Samples will be collected, labelled, stored and shipped as detailed in the Laboratory Manual.

6.6.2 Determination of drug concentration in pharmacokinetic samples

Samples for determination of AZD9291 (and metabolite) concentrations in plasma will be analysed by on behalf of AstraZeneca, using an appropriate bioanalytical method. Full details of the analytical method used will be described in a separate bioanalytical report.

All samples still within the known stability of the analytes of interest (ie, AZD9291 and its metabolites AZ5104 and AZ7550) at the time of receipt by the bioanalytical laboratory will be analysed.

In addition, the pharmacokinetic samples may be subjected to further analyses by AstraZeneca in order to further investigate the presence and/or identity of additional drug metabolites. Any results from such analyses will be reported separately from the Clinical Study Report.

Details on sample processing, handling, shipment and sorage are provided in the Laboratory Manual.

6.7 Pharmacodynamics

6.7.1 Collection of pharmacodynamic assessments

Details on sample processing, handling, shipment and storage are provided in the Laboratory Manual. For sample schedule, see Study Plan (Table 2, Table 3 and Table 4)

6.8 Exploratory research

6.8.1 Exploratory biomarker research

If a patient agrees to participate in the exploratory biomarker research component of the study biological samples (eg, plasma, serum, archived and study-obtained tumour, etc) will be collected and may be analysed for exploratory biomarkers to assess correlations with disease activity, effects of study drug and clinical outcomes.

The results of this exploratory biomarker research will be reported separately and will not form part of the Clinical Study Report.

The results of this exploratory biomarker research may be pooled with biomarker data from other studies with the study drug to generate hypotheses to be tested in future studies.

6.8.1.1 Collection of tumour biopsy samples

All patients will be asked to provide consent to supply a sample of their archival tumour blocks if a sample taken at the time of diagnosis is available. Any archival biopsy samples taken following previous lines of therapy will also be requested, if available. In each case the previous patient treatment must be clearly indicated for each sample provided.

For timings of biopsies see Table 6 below.

Table 6Tumour biopsy samples

Time Relative to dose	Escalation	Expansions	Ph II Extension	Paired Biopsy				
Archival	M *	M *	M *	M *				
Screening	0	M + O	M + O	M + O				
Day 15	0	0	0	М				
Discontinuation	0	0	0	0				
M = Mandatory	O = Optiona	l M* = mandatory if available						

All patients will be asked to consent to optional biopsies as detailed in Table 6. These biopsy samples will be used to support the development of the diagnostic assay and further

exploratory research.

The optional screening sample should be obtained at the same time and as part of the same sample procedure as the mandatory biopsy for T790M status.

For patients in the paired biopsy cohort the mandatory screening biopsy will be used as the 1st of their Paired Biopsies as well as for identifying T790M status.

Tumour samples will preferably be in the form of a formalin fixed paraffin embedded block (tissue derived from the diagnostic tumour or a metastatic site). If this is not possible, 10-20 slides of freshly prepared unstained 5 micron sections from the archival tumour block may be provided.

The biomarkers to be investigated using tumour samples collected from the paired biopsy cohort will not necessarily be limited to but will include all or some of the following:

- pEGFR
- pERK
- pAKT
- pPRAS40
- pS6
- PGSK3β
- P4EBP1
- Cleaved caspase 3

• Ki67

Further details on sample processing, handling and shipment are provided in the Laboratory Manual.

6.8.1.2 Collection of plasma for exploratory analysis of cfDNA

All patients will be requested to provide plasma samples. These samples will be used for the extraction and analysis of circulating free tumour DNA (cfDNA). The sample may be used to further investigate the relationship between PK and blood-borne biomarkers.

Plasma samples will be taken at the following times:

Screening

Pre-dose Day 1

Every 6 weeks up to and including progression (corresponding with the RECIST assessments)

Discontinuation of treatment

The samples will be analysed for a range of oncology biomarkers which may correlate with drug response.

Details on sample processing, handling, shipment and storage are provided in the Laboratory Manual.

6.8.2 Pharmacogenetics

If a patient agrees to participate in the host pharmacogenetics research component of the study a blood sample will be collected. The results of this pharmacogenetic research will be reported separately and will not form part of the Clinical Study Report.

6.8.2.1 Collection of pharmacogenetic samples

The blood sample for genetic research will be obtained from the patients immediately prior to the first administration of AZD9291 in the study. Although genotype is a stable parameter, early sample collection is preferred to avoid introducing bias through excluding patients who may withdraw due to an adverse event. Such patients would be important to include in any genetic analysis. If for any reason the sample is not drawn prior to dosing it may be taken at any visit until the last study visit. Only one sample should be collected per patient for genetics during the study. Samples will be collected, labelled, stored and shipped as detailed in the Laboratory Manual.

6.8.3 Collection of cerebrospinal fluid (optional)

If the patient agrees a sample of CSF will be obtained at one time point taken at any time from Cycle 2 day 1 onwards. Samples will be collected, labelled and stored and shipped as detailed in the laboratory manual.

Any residual CSF after PK analysis may be used for exploratory research into factors that may influence development of NSCLC and/or response to AZD9291.

6.9 **Biological sampling procedures**

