1.3 Exploratory objective(s)

To collect and store plasma for potential exploratory research of blood borne biomarkers into factors that may influence development of NSCLC and/or response to AZD9291 (where response is defined broadly to include efficacy, tolerability or safety).

To collect and store deoxyribonucleic acid (DNA) for future exploratory research into genes/genetic variation that may influence PK or response (ie, absorption, distribution, metabolism, excretion, safety, tolerability and efficacy) to AZD9291 treatment and/or susceptibility to cancers.

To collect and store diagnostic tumour sample and any fresh tumour biopsies for potential future exploratory research into factors that may influence development of NSCLC and/or responses to AZD9291 (where response is defined broadly to include efficacy, tolerability or safety).

To collect patient reported outcomes (PRO) data to explore disease-related symptoms and health related quality of life (HRQoL).

To explore the relationship between PK and selected endpoints (which may include PRO and blood borne biomarkers), where deemed appropriate.

To explore patients' self-perceived side-effects, their importance and how they are valued in relation to treatment effect using patient tolerability interviews.

To characterise the pharmacokinetics (PK) of AZD9291 and its metabolites (AZ5104 and AZ7550) in cerebrospinal fluid (CSF).

To collect and store residual CSF for potential exploratory research of factors that may influence development of NSCLC and/or response to AZD9291 (where response is defined broadly to include efficacy, tolerability or safety).

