The efficacy assessments of objective response (OR), duration of response (DoR), disease control rate (DCR), progression-free survival (PFS) as assessed by RECIST 1.1 and overall survival (OS) are widely accepted parameters for the assessment of efficacy for advanced NSCLC treated with EGFR TKIs (Sun et al 2010).

Preclinical data (Investigator Brochure Section 4.1.1.2) demonstrates that when the clinical efficacy in a dual mutation (L858R/T790M+) mouse xenograft model eventually develops resistance to low dose AZD9291 (1mg/kg/day) a dose escalation (to 25mg/kg/day) reverses the tumour regrowth and provides additional durable sustained tumour shrinkage. Therefore, an increase in dose of AZD9291 to a currently identified well tolerated dose (80 mg) in patients with initial objective responses but subsequent RECIST confirmed disease progression at a lower dose may have the potential to provide prolongation of the clinical benefit for these patients.

The collection of cerebrospinal fluid (CSF) will enable the investigation of the ability of AZD9291 to cross the blood brain barrier. Brain metastases occur in 20-30% of patients with advanced NSCLC, and are associated with poor prognosis (Porta 2011). The first generation EGFR TKI agents have demonstrated only limited efficacy in treating brain metastases (Bai 2013, Ranson 2013, Shimato 2006) however, preclinical data suggests that AZD9291 may be capable of crossing the blood brain barrier (Investigator Brochure) and potentially may offer better exposures in this anatomically protected location.

The collection of samples to allow investigation of the presence and/or identity of metabolites of AZD9291 and, if appropriate, characterise their pharmacokinetics will generate data to allow AstraZeneca to fulfil regulatory requirements related to the testing of the safety of metabolites.

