7.5 Calculation or derivation of pharmacodynamic variables

7.5.1 Population analysis of pharmacokinetic/pharmacodynamic variables

The plasma concentration data for AZD9291 (and the metabolites AZ5104 and AZ7550) will be analysed using a population pharmacokinetic approach, which may include exploring the influence of covariates on PK, if the data allows. A population pharmacodynamic approach will be used to investigate the relationship between PK and selected primary, secondary and/or exploratory endpoints, where deemed appropriate. Results may be reported separately from the Clinical Study Report for the main study.

The pharmacokinetic, pharmacodynamic, demographic, safety and tumour response data collected in this study may also be combined with similar data from other studies and explored using population pharmacokinetic and/or pharmacokinetic-pharmacodynamic methods. The results of any such analyses will be reported separately from the Clinical Study Report.

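### For CSF taken after Cycle 2 Day 2, no concurrent plasma PK sample is scheduled, so the CSF:plasma ratio can only be estimated, not observed

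*Protocol*

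**What the plan says.** Section 6.8.3 makes CSF collection optional and states that "a sample of CSF will be obtained at one time point taken at any time from Cycle 2 day 1 onwards". It gives no time after dose and no latest date, and it does not mention plasma. On handling it says only that "Samples will be collected, labelled and stored and shipped as detailed in the laboratory manual". Study Plan Tables 2, 3 and 4 mark the CSF sample as once only.

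Two places give the purpose. Section 1.3 lists, among the exploratory objectives, the pharmacokinetics of the parent drug and its two metabolites in CSF. Section 3.2 goes further: "The collection of cerebrospinal fluid (CSF) will enable the investigation of the ability of AZD9291 to cross the blood brain barrier". It adds that the drug may reach better exposures in the brain than earlier agents.

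Section 6.6.1 takes plasma PK samples at the times in Table 5. The last of these is 24 h after the Cycle 2 Day 1 dose, and the study plans likewise restrict later PK sampling to Cycle 2. Table 5 does have one event-linked row, "At time of biopsy", for the Cycle 1 Day 15 tumour biopsy. Its footnote says that this "PK sample is only required if biopsy taken and, where optional, is feasible to do so". There is no such row for CSF.

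**The concern.** A CSF concentration on its own shows that drug is present. It does not show how much of the circulating drug gets through, and Section 3.2 raises that question when it speaks of exposure in a protected site. A low CSF value could mean poor penetration, or it could mean that plasma was low at that moment because the draw was near trough, the dose had been reduced or doses had been missed. A plasma level from the same time separates these explanations.

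The protocol applies this logic to tumour tissue: it asks for plasma at the biopsy even though a pre-dose PK sample is already taken that day. For CSF, where a same-day plasma PK sample is not assured, it asks for nothing. Consenting patients would undergo an invasive procedure, and the comparator that makes the result quantitative may never be collected.

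**Working it through.** The protocol states no figure for this point, so the check compares the schedules and then asks how much an estimated plasma level could mislead.

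**1. Where the schedules overlap.** A cycle is 21 days (Section 5.1.1), so Cycle 2 Day 1 is day 22 of multiple dosing. Table 5 samples plasma that day at pre-dose, 1, 1.5, 2, 4, 6, 8, 10 and 12 h, and at 24 h on day 23: ten points. A CSF draw within that window has a plasma comparator. A draw after day 23 has none.

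**2. How long the gap can be.** Section 6.8.3 sets no upper limit. Section 5.2 reports treatment for up to at least 10 months. At 30.4 days per month (assumed), 10 months is 10 × 30.4 = 304 days, and the gap is 304 − 23 = 281 days.

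**3. Error from ignoring time after dose.** The protocol gives no human half-life or tmax. Section 5.3.2 presumes steady state at Day 8 of continuous dosing. If the intervening 7 days (168 h) are 4 to 5 half-lives, the half-life is 168/5 = 33.6 h to 168/4 = 42 h. With an assumed tmax of 4 to 8 h and a one-compartment oral model dosed every 24 h:

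| Half-life (h) | tmax (h) | Peak/trough, tmax read as single-dose | Peak/trough, tmax read as steady-state |
|---|---|---|---|
| 33.6 | 4 | 1.51 | 1.46 |
| 33.6 | 8 | 1.39 | 1.23 |
| 42 | 4 | 1.39 | 1.36 |
| 42 | 8 | 1.31 | 1.19 |

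Across these cases plasma stays between 0.79 and 1.19 times its interval average. On these assumptions, ignoring clock time costs about 20% against average plasma. That is modest, and it shrinks further if the times are known.

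**4. Dose changes between the Cycle 2 profile and the CSF draw.** Section 5.1.6.2 allows extension patients to go from 80 mg to 40 mg, a factor of 80/40 = 2. Section 5.1.1 allows some patients started below 80 mg to be raised to at most 80 mg after at least 6 months; from 20 mg that is a factor of up to 80/20 = 4. These are known quantities, not random error. Section 5.1.8 records treatment details for each patient, so the earlier profile can be rescaled if PK is linear in dose. That linearity is an assumption.

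**5. What stays open.** Recent missed doses, interruptions and change within a patient over months are not captured by a Cycle 2 profile. The documents give no figure for them. Section 6.6.1 requires the date and time of each sample and of the dose, but in the context of the venous blood samples. Section 6.8.3 does not state this for CSF.

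**The case against.** The strongest reply is that the CSF data remain usable. A draw on Cycle 2 Day 1 is allowed and falls on a full plasma profile. For later draws, the patient's own profile gives plasma at a matching time after dose. Section 7.5.1 also says that the plasma data for the parent and both metabolites "will be analysed using a population pharmacokinetic approach, which may include exploring the influence of covariates on PK", and such a model can predict plasma at a recorded time. Measurable drug in CSF is itself qualitative evidence of crossing, and no CSF:plasma ratio is named among the objectives, endpoints or PK parameters. All of this stands. A reader might infer from the missing sample that penetration cannot be derived at all; the documents do not support that. Nor do they support a several-fold uncertainty in the ratio: such a figure needs an assumed half-life and tmax, and then counts a recorded dose change as if it were unknown.

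What remains is narrower. Nothing directs sites to draw CSF on Cycle 2 Day 1, so pairing there happens by chance. A model prediction long after the last plasma PK sample is weaker than a measurement, and it needs dose and sampling times that Section 6.8.3 does not request.

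Two further replies carry less weight. The Laboratory Manual is not shown, but Section 6.8.3 cites it for collection and handling, while the protocol places the plasma schedule in Table 5. Section 6.6.1 says "The timing of the pharmacokinetic samples may be adjusted during the study, dependent on emerging data"; this is general permission and does not tie any sample to the CSF draw.

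**Conclusion.** The point holds in limited form and is minor. Followed as written, the plan provides no observed CSF:plasma ratio of AZD9291, AZ5104 or AZ7550 for any CSF sample taken after Cycle 2 Day 2. Whether drug reaches the CSF can still be answered. How much reaches it can only be estimated, and the estimate is weaker after dose changes, interruptions or missed doses. Under the assumed half-life and tmax, the timing error alone is about 20% of average plasma; the remaining error cannot be sized from the documents. No primary or secondary endpoint, dose decision or sample size is affected. The conclusion rests on Table 5 being the complete plasma PK schedule, as Section 6.6.1 presents it. If the Laboratory Manual already requires plasma at the CSF draw, only the protocol text needs aligning.

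**What to change.** Add a row to Table 5 and a sentence to Section 6.8.3 requiring one plasma PK sample at the time of the CSF draw, modelled on the biopsy row. Record the date and time of the CSF sample, the plasma sample and the last dose. State that the CSF:plasma ratio of the parent and both metabolites will be reported from the paired values. Mark the CSF row in the study plans accordingly.

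The cost is one small extra blood draw in consenting patients who are already having the procedure, and none if the CSF is taken during the Cycle 2 Day 1 profile. Restricting all CSF draws to that profile would also secure pairing, but it would limit when an optional sample can be obtained, so the paired plasma sample is the better choice. The change has to come before the CSF is drawn, because the concurrent plasma level cannot be recovered afterwards.

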6.9.1 Volume of blood

The number of samples taken, as well as the volume required for each analysis, may be changed during the study as new data on AZD9291 become available. The estimated total volume of blood that will be drawn from each patient in this study for mandatory samples up to the end of Cycle 2 is; dose escalation 150ml, dose expansion 100ml and dose extension 70ml

Safety laboratory assessments will be performed locally at each centre's laboratory by means of their established methods. The number of samples/blood volumes is therefore subject to site-specific change.

6.9.2 Handling, storage and destruction of biological samples

The samples will be used up, or disposed of after analyses or retained for further use as described below.

Any pharmacokinetic sample remaining after analysis for AZD9291 and its metabolites may be used for exploratory biomarker analyses. These analyses are for AstraZeneca use only and will not be included in the Clinical Study Report.

Biological samples for future research will be retained at AstraZeneca or it's designee for a maximum of 15 years following the finalisation of the Clinical Study Report. The results from future analysis will not be reported in the Clinical Study Report but separately in a bioanalytical method validation report.

6.9.2.1 Pharmacokinetic samples

Incurred sample reproducibility analysis, if any, will be performed alongside the bioanalysis of the test samples and reported in a separate bioanalytical report.

Key samples for metabolite identification and/or analysis will be retained at

, on behalf of Drug Metabolism and Pharmacokinetics (DMPK), AstraZeneca for a maximum of one year following the finalisation of the Clinical Study Report. The results from the investigation will not be reported in the Clinical Study Report but separately in a DMPK report.

6.9.2.2 Samples for exploratory research

Details of sample collection, processing, shipping and storage will be described in the Laboratory Manual.

Each sample for exploratory research will be identified with the study number and patient enrolment number. In this way exploratory biomarker and genetic data may be correlated with clinical data, samples destroyed in the case of withdrawal of consent and regulatory audit enabled.

Where genetic analysis will be undertaken the processes adopted for the coding and storage of samples will be more stringent in order to maintain patient confidentiality. As an added precaution, irrespective of the type of sample, the DNA sample will be assigned a unique number replacing the information on the sample tube. Thereafter, the DNA sample will be identifiable by the unique DNA number only. The DNA number will be used to identify the sample and corresponding data at the AstraZeneca genetics laboratories, or at the designated contract laboratory. No personal details identifying the individual will be available to any person (AstraZeneca employee or contract laboratory staff) working with the DNA.

The samples and data for genetic analysis in this study will be single coded. The link between the patient enrolment code and the DNA number will be maintained and stored in a secure environment, with restricted access within the Clinical Genotyping Group Laboratory Information Management System (LIMS) at AstraZeneca. The link will be used to identify the relevant DNA samples for analysis, facilitate correlation of genotypic results with clinical data, allow regulatory audit and to trace samples for destruction in the case of withdrawal of consent when the patient has requested disposal/destruction of collected samples not yet analysed.

